3.5. Randomization

This pilot study will recruit 90, youth with ASD ages 8-11 years old into a randomized, parallel group design of 1) ION-ASD and 2) control group – facilitated play. A feasibility trial will be conducted with the first 10 participants to refine the protocol including finalizing measures to support Aim 2 (brain-based behavior

Confidential

Rush University Medical Center

toolbox). If substantial protocol revisions are made, modifications to the protocol, consent, and IND will be made before proceeding with recruitment.

Participants will be randomized 1:1 to ION-ASD or control. After eligibility is confirmed and consent is obtained, eligible participants will be assigned a study randomization number according to computer-generated randomization list.

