3.7. Participant Withdrawal Criteria

Participants will be withdrawn from the study treatment if they meet one or more of the following criteria:

1. CGI-I ≥ 6 on two consecutive visits
2. If they become pregnant during the study
3. If they have blood pressure above 99th percentile for age, gender, and height on two consecutive visits (*range in accordance with the Fourth Report on the Diagnosis, Evaluation, and Treatment of High Blood Pressure in Children and Adolescents (U.S. Department of Health and Human Services)⁵³)
4. If they have blood pressure above the 99th percentile for age, gender, and height on two consecutive visits
5. If they experience an adverse event that is deemed by the Medical Independent Evaluator (IE) to be an unacceptable safety risk
 - o If the Study clinician feels it is in the participant's best interest to discontinue the study treatment

4. Study Assessments

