4.2. Efficacy Assessments

Efficacy assessments will be evaluated through questionnaires, direct assessments of social cognition, and questionnaires surveying quality of life, social functioning, anxiety, & repetitive behaviors.

Primary Outcome Measures. This study has two primary outcomes reflective of the dual treatment targets to underlie social learning in school-age children: social cognition and social behavior. Each outcome will be measured by a composite score developed through a factor analysis of measures in each domain in the Seaver-NET RCT¹⁶.

1. Social Behavior Composite. (Baseline, Week 12, Week 16, Week 20)
 - a. *Children's Communication Checklist (CCC)*⁵⁵. The CCC⁵⁵ is a 70-item caregiver rating scale which includes language scales (e.g. speech, syntax) and pragmatic scales (e.g. scripted language, nonverbal communication, social relations).
 - b. *Griffith Empathy Scale*.⁵⁶ The Griffith Empathy Measure⁰ is a 23-item caregiver rating scale that assesses both affective and cognitive empathy in children and adolescents. The measure was adapted from Bryant's Index of Empathy³² by Dadds and colleagues.
2. Social Cognition Composite (Baseline, Week 12, Week 16, Week 20)
 - a. *Reading Mind in Eyes Test (RMET)*. The RMET examines an individual's ability to determine what a person is thinking or feeling based on photographs of the eye region of male and female faces. A computerized, combined child and adult version of the RMET will be used in the trial reflecting clinical measurements employed in a larger, NIH-funded monotherapy trial of oxytocin vs. placebo⁵⁷.
 - b. *Diagnostic Analysis of Nonverbal Accuracy-2 (DANVA2)*⁵⁸. The DANVA2 examines emotion recognition using both visual and auditory stimuli. Participants were administered all subtests of the DANVA2.

Secondary Outcome Measures. While functional improvements are not expected to be clinically significant within the brief intervention, we will assess changes in social and quality of life metrics as secondary outcomes with the following measures.

1. Global functioning

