*Clinical Global Impressions – Improvement Scale - Global (CGI-I)*⁵⁴. The CGI-I employs a seven point (1 = very much improved to 7 = very much worse) to determine the patient's improvement in response to treatment. The CGI-I has been successfully used as an outcome measure in previous psychopharmacology trials including the RUPP trial of risperidone in children with ASD, and the STAART funded citalopram trial. The rating convention for assigning CGI scores is to use all available data including direct observation, scales, and patient report to inform clinical judgment. CGI-I, Global will be used to evaluate safety, with the requirement that individuals scoring CGI of 6 or greater for 2 or more weeks be discontinued from the study and provided with appropriate referrals. CGI ratings will be made by unblinded clinicians conducting safety evaluations and blinded raters.

Blinded CGI-I ratings will incorporate semi-structured questions to evaluate social conversational and social behavioral skills. Questions will be based on the Bates & Reilly conversational task (Reilly, Bates, & Marchman, 1998). Blinded CGI ratings will be recorded to code narrative discourse and quality in collaboration with the social communication lab of [name]. Social Functioning

2. Social functioning

- a. *Social Skills Improvement System (SSIS)*. The SSIS is an informant-report that evaluates social skills, problem behaviors, and academic competence in youth ages 3-18 years old. The SSIS is a multi-rater with reports provided by caregivers, teachers, and students. The form takes 10-25 minutes to complete. The scale is designed to identify social impairments for intervention development and tracking.

3. Quality of Life

- a. *Caregiver Strain*⁵⁹. The CSQ assess family stress and was developed for caregivers of children with developmental disabilities.

Exploratory Outcome Measures

1. Social Function

- a. *Autism Impact Measure*⁶⁰. The AIM is a 25-item caregiver report assessment of the frequency and impact of core ASD symptoms in children with ASD. This new measure is designed to assess recall of core symptoms within two-week intervals and will be used as an exploratory measure of changes in core ASD symptom presentation in this study.

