8.9. Sample size considerations

Based on data from the NETT trial, published trials in sustained OT treatment⁵⁴, and single-dose challenge studies in autism⁴⁹ we expect our sample size (n=25/group with 5% attrition) to yield 80% power to detect a difference in means of 0.40, assuming a standard deviation of differences of 0.670, with a 0.050 two-sided significance level. Although potentially underpowered, we believe data from this trial will provide important information on safety, tolerability, and treatment targets from a novel, multi-dosing OT-combined treatment strategy. Specific Aim 2 (treatment targets, pre-treatment factors predictors). Repeated measures ANOVAs will be conducted to evaluate group differences on social behavior and social cognition composites, social recognition, mental state inference, affiliation, social reward and social competence (i.e. SSIS) in order to identify potential treatment targets for the combined treatment approach. Factors predicting treatment response will include global scores on all baseline measures. Responder status will be entered as a categorical variable as defined above (CGI-I≤2 + SSIS > 25%). PCA will be conducted on significant baseline predictors to develop composite variables and used to predict response using logistic regression.

Confidential

Rush University Medical Center

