Data Analysis. Primary: Composite scores of both primary outcomes (i.e., SBI and SC) will be used as the response (i.e., outcome) variable in a series of mixed-effects linear regression models using the *lmer* package in *R Studio* to assess the effect of treatment condition (ION-ASD vs. Facilitated Play), time (e.g., change from baseline after 12 weeks), and condition X time interaction. Across all models, the individual participant will be included as the random effect. Age, verbal IQ, ADHD and generalized anxiety (from the Child & Adolescent Symptom Inventory-5 [CASI-5] T-scores) will be entered into the model to be examined as potential covariates and/or moderators to outcomes as in prior work. We will estimate effect sizes (standardized Betas) and confidence intervals (95%) acknowledging the likelihood that analyses may not permit definitive conclusions given the likely size of the confidence intervals. Finally, if the statistical assumptions of the model are not met (e.g., homoscedasticity, normality, linear relationships), generalized linear models with appropriate link functions or potential transformations of predictor variables will be assessed.

Secondary Outcomes. The linear mixed-effects models will also be used on secondary outcome measures: SRS T-score, mean Caregiver Strain Global rating scale. Responder (i.e., Clinical Global Inventory-Improvement [CGI-I]) analysis will be conducted using either a Chi-squared or Fisher's exact test (when observations are small such that $>20\%$ of cells have *expected* count <5) on the number of responders (i.e., CGI-I scores of 1-2) versus non-responders (i.e., CGI-I scores of 5-7) by group.

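### The SAP's responder test compares CGI-I 1-2 with 5-7, so children rated 3 or 4 drop out and a real difference in response can be hidden

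*SAP*

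**What the plan says.** The SAP, under Data Analysis, Secondary Outcomes, says that the responder "analysis will be conducted using either a Chi-squared or Fisher's exact test". Fisher's test is used when more than 20% of cells have an expected count below 5. The comparison is made "on the number of responders (i.e., CGI-I scores of 1-2) versus non-responders (i.e., CGI-I scores of 5-7) by group". Both groups are introduced by "i.e.", so these are definitions and not examples.

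Protocol section 4.2 describes the scale: "The CGI-I employs a seven point (1 = very much improved to 7 = very much worse". Ratings of 3 and 4 are therefore valid. No sentence in either document assigns them to a cell or says how those children are handled.

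Protocol sections 2.2 and 8.9 hold another responder definition, which combines the CGI-I with a 25% change on the SSIS. It serves the Aim 2 prediction analysis and does not mention 5-7 as a comparator.

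**The concern.** Under the SAP text, an analyst builds a 2x2 table that leaves out two of the seven ratings. Whether a child is rated 3 or 4 is known only after randomisation and may depend on treatment. Removing those children conditions the comparison on an outcome, so the groups compared are no longer the randomised ones. The question changes from how many children responded to how many responded among those whose rating moved clearly either way.

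Two parts of the protocol suggest that the omitted group could be large and the 5-7 cell small, although neither gives a distribution. Section 4.2 introduces the secondary outcomes with "While functional improvements are not expected to be clinically significant within the brief intervention". Section 3.7 withdraws a child from study treatment for "CGI-I ≥ 6 on two consecutive visits". If no child is rated 5-7, the table has an empty column and no test can be done.

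A true difference in response could be missed, the estimate could point the wrong way, or a difference in worsening could be reported as a difference in response.

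**Working it through.** **Inputs from the documents.** The cells and the test rule come from the SAP. Allocation is equal (Protocol 3.5: "Participants will be randomized 1:1 to ION-ASD or control"). Group size is 35 per arm from the Phase 2 total of 70 (Protocol 3.1), or 25 per arm from the power statement (Protocol 8.9). The level is 0.05 two-sided; section 8.9 states it for the composite comparison, and it is assumed here for the responder test. The documents give no response rate or power for this test, so there is no figure of theirs to reproduce.

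**Assumed inputs.** All CGI-I rates below are hypothetical.

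**Step 1: what is compared.** Let p12 and p57 be the shares rated 1-2 and 5-7 in an arm. The written test compares p12 / (p12 + p57) between arms; the usual responder test compares p12. With p12 of 40% versus 15%:
- p57 = 5% in both arms: 0.40/0.45 = 89% versus 0.15/0.20 = 75%
- p57 = 10% in both arms: 0.40/0.50 = 80% versus 0.15/0.25 = 60%
- p57 = 20% in both arms: 0.40/0.60 = 67% versus 0.15/0.35 = 43%

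**Step 2: children used.** At 35 per arm the expected number in the table is 35 × (0.45 + 0.20) = 22.75, 35 × (0.50 + 0.25) = 26.25 and 35 × (0.60 + 0.35) = 33.25. That is about 23, 26 and 33 of 70.

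**Step 3: power under the SAP's own test rule.** Exact enumeration of the three outcomes in each arm, chi-squared without continuity correction, response 40% versus 15%:

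| Per arm | Rated 5-7, both arms | Power as written | Power, all children | Wrong-direction estimate, as written | Wrong-direction estimate, all children |
|---|---|---|---|---|---|
| 35 | 5% | 8% | 66% | 23% | 0.5% |
| 35 | 10% | 14% | 66% | 15% | 0.5% |
| 35 | 20% | 24% | 66% | 9% | 0.5% |
| 25 | 5% | 5% | 53% | 26% | 1.3% |
| 25 | 10% | 10% | 53% | 19% | 1.3% |
| 25 | 20% | 15% | 53% | 13% | 1.3% |

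At 25 per arm with 5% rated 5-7, no test is possible in 8% of trials. Nearly all of this is the chance that no child is rated 5-7: 0.95^50 = 7.7%.

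**Step 4: unequal shares rated 5-7.** Simulation, 35 per arm, same response rates (ION-ASD versus control):

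| Rated 5-7 | Power as written | Power, all children |
|---|---|---|
| 5% vs 15% | 51% | 66% |
| 5% vs 20% | about 70% | 66% |
| 5% vs 25% | 82% | 66% |

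**Step 5: equal response.** With 30% rated 1-2 in both arms and 5% versus 25% rated 5-7, the written test compares 0.30/0.35 = 86% with 0.30/0.55 = 55%. It rejects in 36% of simulated trials at 35 per arm, against 5% when all children count.

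**Step 6: two constructed tables, 35 per arm** (counts rated 1-2 / 3-4 / 5-7).
- ION-ASD 16/17/2, control 7/26/2. As written: 16/18 = 89% versus 7/9 = 78%, Fisher p = 0.58, with 27 of 70 children. All children: 16/35 = 46% versus 7/35 = 20%, chi-squared p = 0.022.
- ION-ASD 14/18/3, control 5/29/1. As written: 14/17 = 82% versus 5/6 = 83%, Fisher p = 1.0, with 23 of 70 children. All children: 14/35 = 40% versus 5/35 = 14%. The smallest expected count is 19 × 35/70 = 9.5, so the SAP rule selects chi-squared: p = 0.016 (Fisher p = 0.030).

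**The case against.** The strongest objection concerns size. The low power figures assume the same share rated 5-7 in both arms, so the 5-7 cell carries no treatment signal. A treatment that produces more responders may also produce fewer children who worsen, and step 4 shows that the loss then shrinks or reverses. This stands: severe power loss is one possible result, not the expected one. It does not rescue the rule, because any gain in power comes from differences in worsening, and step 5 shows the same mechanism producing a false finding on response.

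The second constructed table also puts more worsened children in the better-responding arm (3 versus 1), which makes it an extreme case. The first has two in each arm and shows the same loss of significance.

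A further objection is that 5-7 is probably a slip for 3-7. The Aim 2 definition in Protocol 8.9 uses a CGI-I cut at 2 with no excluded middle, which makes this plausible. That definition belongs to a different analysis, though, and does not correct the SAP. If the wording stays, the handling of 3 and 4 could be decided after the data are seen.

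Finally, this is a secondary outcome in a pilot whose documents already warn that conclusions may not be definitive. That limits the stakes, but it does not justify a test aimed at the wrong quantity.

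**Conclusion.** The concern holds. As written, the SAP omits children rated 3 or 4 and tests a quantity that is not the response rate. A real difference can be hidden: in the equal-worsening scenarios, power falls from 66% to between 8% and 24% at 35 per arm, and from 53% to between 5% and 15% at 25 per arm. The error can also run the other way and create a difference where response is equal.

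These sizes depend wholly on assumed CGI-I rates. That the categories leave a gap, and that the gap changes what is tested, does not depend on them. The point should be fixed, whether 5-7 was intended or is a slip. It touches the CGI-I responder analysis only.

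**What to change.** In the SAP's Secondary Outcomes paragraph, define responder as CGI-I 1-2 and non-responder as CGI-I 3-7, with every child who has a rating at the analysed visit in the denominator. This is one line of wording and needs no new data. Reported response percentages will be lower than with 3 and 4 left out.

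Two additions are worth making in the same edit, although the main correction does not depend on them:
- Name the visit and the rating, preferably the blinded Week 12 rating. The SAP names neither, and Protocol 4.2 provides for both blinded and unblinded ratings.
- Add a sensitivity analysis on all randomised children that counts a missing rating as non-response.

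The Aim 2 responder definition (CGI-I plus SSIS) can stay, if the SAP states that it is a separate definition.
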